5.1.3 Participant Follow-up

Participants are expected to be followed from the date of first dose of AC699 until the end of the study or death, whichever occurs first. Participants who discontinue the study treatment will continue to be followed up for disease progression (after the 30-day safety follow-up) through the end of the whole study as per the Protocol section 7.4.3: follow-up visits will be performed every 8 weeks (± 5 days) for the first year after treatment ends and then every 16 weeks (±5 days) thereafter until disease progression based on RECIST 1.1 or another withdrawal criterion is met:

- Start of a new anti-cancer therapy
- Lost to follow-up

Page 18 of 28

- Death
- Patient withdrawal
- End of the whole study

5.2 **Endpoints**

5.2.1 **Best Overall Response**

Best overall response (BOR) is defined as per RECIST 1.1 and will be calculated as the best response recorded from date of first dose of AC699 up until evidence of progression per RECIST 1.1.

The frequency and percentage of participants with each response will be summarized.

Confirmation of response is required (i.e., consecutive CRs, consecutive PRs or 1 CR and PR at least 4 weeks apart).

See Table 3 for scenarios of overall response.

Table 3: Best Overall Response with Confirmation of CR and PR Required

Overall Response			
Initial Subsequent		BEST Overall Response	
CR	CR	CR	
CR	PR	SD, PD, or PR*	
CR	SD	SD if minimum criteria for SD duration met, otherwise PD	
CR	PD	SD if minimum criteria for SD duration met, otherwise PD	
CR	Missing	SD if minimum criteria for SD duration met, otherwise NE	
PR	PR	PR	
PR	CR	PR	
PR	SD	SD	
PR	PD	SD if minimum criteria for SD duration met, otherwise PD	
PR	Missing	SD if minimum criteria for SD duration met, otherwise NE	

Abbreviations: CR = complete response, PR = partial response, SD = stable disease, PD = progressive disease, NE = not evaluable

When SD is believed to be the BOR, SD must have met the minimum interval of 7 weeks (8 weeks - 1 week for early assessments within window) since start of AC699. If it does not

^{*}If a CR is truly met at first time point, then any disease seen at a subsequent time point, even disease meeting PR criteria relative to baseline, makes the disease PD at that point (since the disease must have reappeared after CR). Best response would depend on whether minimum duration of SD was met. However, sometimes 'CR' may be claimed when subsequent scans suggest small lesions were likely still present and in fact the patient had PR, not CR at the first time point. Under these circumstances, the original CR should be changed to PR and the best response is PR.

meet the minimum interval and there are no subsequent assessments indicating the participant had a PD, the BOR would be NE.

If a CR or PR cannot be confirmed, the BOR is dependent on the subsequent timepoint response. If the subsequent timepoint response is NE or there is no subsequent timepoint response, the BOR would be SD provided the minimum criteria for SD duration is met, otherwise NE. The unconfirmed responses (unconfirmed CR and unconfirmed PR) will be summarized as a sub-category of SD, and SD not meeting the minimum interval of 7 weeks (8 weeks – 1 week for early assessments within window) will be summarized as a subcategory of NE.

5.2.2 **Objective Tumor Response**

The following endpoints, along with their 95% CI, will be presented based on the objective tumor response:

- ORR = proportion of participants with a BOR of confirmed CR or PR.
- CBR = proportion of participants with a confirmed CR, or PR or a SD for ≥ 6 months according to the RECIST 1.1 criteria, where duration of SD is defined the date of last SD assessment the start date of study drug.
- DCR = proportion of patients with a best overall response of CR, PR, or SD (where SD is >= 6 months).

The denominator will be the number of participants in the EFF analysis set, and includes participants with a BOR of NE.

5.2.3 **Duration of Response**

Only participants with measurable disease whose BOR is CR or PR will be included in the analysis.

DoR (months) is defined as the time from first documentation of response (CR or PR, subsequently confirmed) to the first documentation of disease progression or death due to any cause. Participants who have neither progressed nor died will be censored.

Refer to **Table 4** for the event/censoring rules and dates to be used.

5.2.4 Progression-Free Survival

PFS (months) is the time from date of first dose of AC699 to the first documentation of disease progression or death due to any cause. Participants who have neither progressed nor died will be censored.

Refer to Table 4 for the event/censoring rules and dates to be used.

Table 4: Progression Situations and Event/Censoring Rules

Situation	Date of Event or Censoring	Outcome
No baseline assessment	Date of first dose of AC699	Censored

Situation	Date of Event or Censoring	Outcome
Progression documented between scheduled visits, or after one missed or non-evaluable assessment	Date of progression (see Table 2)	Event
No progression	Date of last evaluable tumor assessment (see Table 2)	Censored
Treatment discontinuation for undocumented progression (e.g., clinical progression based on investigator claim)	Date of last evaluable tumor assessment (see Table 2)	Censored
Treatment discontinuation for adverse event or other reason	Date of last evaluable tumor assessment (see Table 2)	Censored
Further anticancer therapy started	Date of last evaluable tumor assessment (see Table 2)	Censored
Death before first PD assessment	Date of last evaluable tumor assessment (see Table 2)	Event (PFS)
Death before the next scheduled tumor assessment, or after one missed tumor assessment	Date of death (see Table 2)	Event (PFS)
Death, or progression after two or more missed tumor assessments	Date of last evaluable tumor assessment (see Table 2)	Censored

The rule to determine whether there are at least two missing tumor assessments is based on the interval between the last evaluable tumor assessment date and the event date. If the interval is greater than twice the protocol-specified interval between the tumor assessment plus the protocol-allowed time window around the assessment, then the number of missing assessments is two or more.

For the first 52 weeks, tumor assessments are to be performed every 8 weeks (\pm 5 days); therefore, the threshold will be 18 weeks. After the first 52 weeks, tumor assessments are to be performed every 16 weeks (\pm 5 days); therefore, the threshold will be 34 weeks.

6 Safety Analysis

All safety data will be presented in listings. Tables and figures will be presented as applicable.

Exposure to Study Treatments

Exposure to AC699 will be summarized in the following ways:

- Total Treatment Duration (days), calculated as *Date of Last AC699 Dose Date of First AC699 Dose + 1*.
- Actual Duration of Exposure (days) calculated as (Date of Last AC699 Dose Date of First AC699 Dose + 1, excluding days where AC699 dose was interrupted, and the participant successfully returned to receiving AC699 or a full AC699 dose was missed.
- Relative Dose Intensity (RDI) (%)

The number of participants with dose interruptions, dose modifications (increased, not changed, reduced, interrupted, withdrawn), and intra-patient dose-escalation together with the reason of interruption/modification will be summarized by frequency and percentage.

Note: Dose interruptions will be summarized up until the last dose where participant received the study treatment. If the last dosing record(s) show an interruption, those will not be included in the summary.

Any overdoses will be listed.

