5.1.2 Time-to-Event Variables

Time-to-event variables are defined as:

Time-to-Event (months) = (End Date - Start Date + 1) / 30.4375

 $DOR = (Earliest\ Date\ of\ Progression\ or\ Death-Date\ of\ First\ Documented\ CR\ of\ PR + 1)/30.4375.$

Start Dates

For all time to event variables other than DoR, the date of first dose of AC699 will be used as the start date.

The start date for DoR will be the date of first PR or CR, which has been subsequently confirmed.

End Dates

For DoR and PFS, the following rules will be used to derive the end dates for these endpoints:

- Events always take precedence to Censoring
- If multiple event dates are applicable, the earliest date will be used.
- If multiple censoring dates are applicable, the latest date will be used.

Table 2 shows data sources that can be used to determine end dates.

Table 2: Data Sources for End Dates

Date	Data Source	
Date of Death	Death CRF	
Date of Progression	Using RECIST 1.1 criteria, the earliest of the dates from the components that triggered the overall PD response from the Target Lesions, Non-target Lesions and New Lesions CRFs.	
Date of Last Evaluable Tumor Assessment	The latest data from the Target Lesions, Non-Target Lesions, and New Lesions CRFs reflecting the overall response, where the overall response is evaluable (i.e., not missing or NE), prior to further subsequent anticancer therapy if initiated.	
Date of Subsequent Anticancer Therapy	The earliest date is from the Subsequent Systemic Therapy, Subsequent Radiation, and Subsequent procedure CRFs.	

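### SAP Table 4 dates one class of PFS deaths at the last scan instead of at death, and an unqualified precedence rule leaves event status undetermined for some late events

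*SAP*

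**What the plan says.** SAP 5.2.4 defines PFS from first dose to "first documentation of disease progression or death due to any cause" and sends the reader to Table 4 for events, censoring and dates. Four Table 4 rows matter here:

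- "Death before first PD assessment": an event, dated at the last evaluable tumor assessment.
- "Death before the next scheduled tumor assessment, or after one missed tumor assessment": an event, dated at death.
- "Death, or progression after two or more missed tumor assessments": censored at the last evaluable assessment.
- "Further anticancer therapy started": censored at the last evaluable assessment.

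SAP 5.1.2 adds general rules for end dates. The first is "Events always take precedence to Censoring", with no exception. Another says that when several event dates apply, the earliest is taken. Table 2 in the same section takes the date of death from the death form. It defines the last evaluable assessment as one with an evaluable overall response, before any subsequent anticancer therapy.

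Protocol 10.4.2 censors only patients who are alive and progression-free. SAP section 8 reports no changes from the protocol's analyses.

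**The concern.** There are two separate faults.

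**Date.** One death row carries a scan date, which contradicts the endpoint definition and the row beside it. The status (event) is right and the time is too short. The phrase describing the row is not defined, so it is also unclear which deaths it covers.

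**Status.** The row for two or more missed assessments applies only to patients who have died or progressed. If events always win, that row and the 18- and 34-week thresholds beneath the table never operate. If the row operates, events do not always win. The new-therapy row raises the same question when progression or death follows new therapy. No text says which rule governs.

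DoR is referred to the same table, and PFS feeds the planned ESR1, CTC and ctDNA correlations. The study is open-label with investigator-assessed response. If the choice is left to programming, it may be made with outcomes known.

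**Working it through.** The plan gives no PFS figure to reproduce, so the check applies its own rules to test patients.

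**Inputs**
- Time in months = (end − start + 1) / 30.4375, with first dose as start (SAP 5.1.2).
- Scans every 8 weeks ± 5 days in the first 52 weeks; the threshold for two or more missed is 18 weeks = 126 days (SAP 5.2.4).
- Baseline scan within 28 days before first dose (protocol Schedule of Assessments, tumor assessment footnote).
- Efficacy analyses use the EFF, which requires an adequate post-baseline response assessment (SAP 3.3).

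With end dates counted as study days (first dose = Day 1), the formula reduces to day / 30.4375.

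**Test 1: the death row, read as no progression documented yet.** Last scan Day 57 without progression, death Day 100. The next scan is due on Day 113 (57 + 56), so both death rows fit.
- Row "Death before first PD assessment": 57 / 30.4375 = 1.87 months.
- Row "Death before the next scheduled tumor assessment, or after one missed tumor assessment": 100 / 30.4375 = 3.29 months.

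The earliest-date rule selects 1.87. The shortening equals the gap from scan to death. It is up to 61 / 30.4375 = 2.0 months for a death within one 8-week interval plus 5 days, and up to 126 / 30.4375 = 4.1 months at the 18-week limit.

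**Test 2: the same row, read as no post-baseline scan.** The only scan is baseline. Taken 28 days before first dose, it gives (−28 + 1) / 30.4375 = −0.89 months; taken 1 day before, it gives 0. If Table 2 is applied strictly, the date is undefined, because a baseline scan has no overall response. A death on Day 40 should give 40 / 30.4375 = 1.31 months. Such patients are mostly outside the EFF.

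**Test 3: precedence.** Last scan Day 57, death Day 197. The gap is 140 days, beyond 126.
- Table 4 governs: censored at 57 / 30.4375 = 1.87 months.
- Precedence governs, with the date of death: event at 197 / 30.4375 = 6.47 months.

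**Effect of the date fault on a dose-level median.** This is an illustrative simulation; its settings are assumptions, not document figures. It uses 20 patients, exponential PFS, 8-weekly scans, everyone followed to an event, and 2,000 samples per setting. Every death without progression is dated either at death or at the last scan. Each cell gives the mean change in the Kaplan-Meier median and the share of samples in which it changes.

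| True median (months) | 5% of events are deaths without PD | 10% | 20% |
|---|---|---|---|
| 4 | −0.04; 6% | −0.09; 12% | −0.17; 25% |
| 6 | −0.02; 6% | −0.06; 12% | −0.11; 25% |
| 9 | −0.02; 7% | −0.04; 13% | −0.13; 25% |

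The simulation keeps deaths before the first scan, dated at time zero; the EFF would mostly drop them.

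**Weight of one patient.** In a dose level of about 20 (protocol), one patient is 1/20 = 5 percentage points.

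**The case against.** The strongest reply on precedence is that it is only a tie-break between Table 4 rows. SAP 5.2.3 and 5.2.4 name Table 4 as the source of the rules, and the missed-scan row could define which late events do not qualify. That is a sensible intention, and it means event status is undetermined, not shown to be wrong. It does not rescue the text, because the word is always and the missed-scan row has no patients other than those with an event. For new therapy the conflict is narrow: follow-up ends when new therapy starts (protocol 5.3 and 7.4.3, SAP 5.1.3), so later progression is mostly not collected.

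Three stronger readings are tempting, and the documents do not support them.

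- *PFS times will be zero or negative.* This needs a patient without an evaluable post-baseline scan, and the EFF excludes most of them. A small residue remains: adequate is not defined, and SAP 5.2.2 keeps patients whose best response is not evaluable. This reading and the two-date overlap in Test 1 also rest on different meanings of the same phrase, so they cannot both be charged against it.
- *Progression found after stopping treatment is thrown away.* The row "Treatment discontinuation for adverse event or other reason" censors at the last evaluable scan, not at treatment stop, and Table 2 has no cut at treatment stop. SAP 5.1.3 says "Participants who discontinue the study treatment will continue to be followed up for disease progression". A progression found then also fits the progression row, and precedence makes it an event.
- *All PFS times and statuses are wrong.* Only particular patients are touched, and the disputed death row has the right status.

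**Conclusion.** The point holds in two parts. First, the date in the row "Death before first PD assessment" contradicts the PFS definition and the adjacent row. Within the EFF it can shorten an affected patient's PFS by up to about 2.0 months for a death within one scan interval and 4.1 months at the 18-week limit. This rests on reading the phrase as no progression documented yet. The average effect on a 20-patient median is small under the assumed settings (0.02 to 0.17 months), although the median changes in 6% to 25% of samples.

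Second, the precedence rule and the missed-scan row cannot both be followed, and the new-therapy row conflicts in the same way for the few patients with a later recorded event. Their status is open until the SAP states an order. How many there will be cannot be told from the documents.

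PFS is a secondary, descriptive endpoint; safety is primary and no hypothesis is tested. No test, sample size or dose-escalation rule depends on this. It is a wording defect to settle before programming and database lock.

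**What to change.** 1. In Table 4, enter the date of death for the row "Death before first PD assessment" and define the phrase, so that each death fits one row.
2. In SAP 5.1.2, replace the unqualified precedence rule with a statement that progression or death is an event, and overrides the other censoring rows including treatment discontinuation, unless it occurs after new anticancer therapy or after two or more missed assessments. In those two cases, censor at the last evaluable assessment before that point.
3. In SAP section 8, list this as a departure from protocol 10.4.2, which censors only patients alive and free of progression.

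The treatment-discontinuation row can stay once the order is stated. The cost is SAP wording and the matching programming; no new data are needed.

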- Tumor assessments should be performed according to Response Evaluation Criteria in Solid Tumors (RECIST) Version 1.1 (see Appendix B) and should include computed tomography (CT) scans of the chest, abdomen, pelvis, and, if clinically indicated, imaging of any other known or suspected sites of disease (e.g., brain, bones) using an appropriate method (CT scan or magnetic resonance imaging [MRI] or bone scintigraphy). An MRI may be performed in place of a CT scan at the discretion of the Investigator. However, the same imaging modality should be used throughout the study to image a given lesion. The same radiographic procedure must be used throughout the study. In case of suspected (but not otherwise confirmed) bone metastasis at screening, tumor assessment at screening should include a bone scan. Correlative imaging should then be repeated at each tumor assessment. Assessments will be performed by the Investigator at screening and after 2 cycles (±5 days) of treatment. Response will be assessed every 2 cycles / 8 weeks (±5 days) for the first 1 year of treatment, and then every 4 cycles / 16 weeks (±5 days) thereafter, at the EOT visit (if not performed within the previous 4 weeks), and at the discretion of the Investigator. Baseline tumor assessments must be performed within 28 days before first drug intake.
- ^o An EOT visit should be performed for all patients who permanently discontinue study treatment. If the decision to permanently discontinue treatment is taken at a scheduled visit, the EOT visit should be performed instead of the scheduled visit (preferably within 7 days and no later than 14 days after the last treatment).
- P All patients will be followed during the off-treatment period until all treatment-related toxicities resolve or stabilize (unless, in the opinion of the Investigator, the AE or laboratory abnormality/ies is/are not likely to improve because of the underlying disease), or 30 days (± 5 days) post-study drug discontinuation, or until the start of another anti-cancer treatment. Any concomitant medications received up to 30 days after the last dose of study drug should be recorded.
- ^q Follow-up for PD visits for tumor assessment by imaging (CT scan or MRI) for patients who discontinue study treatment without having PD based on RECIST v1.1 (see Appendix B) should be performed as on treatment until PD or another withdrawal criterion is met (see Section 5.2).

Sponsor/Development Innovations Study Numbers: AC699-001/BRE 401

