7.4.3 Extended Follow-Up Period

Patients discontinuing study treatment for reasons other than radiographic disease progression will began an extended follow-up period to continue monitoring disease status (after the 30-day safety follow-up). The response assessments will be performed every 8 weeks (\pm 5 days) (from the patient's initial Cycle 1 Day 1 visit) for the first year and then every 16 weeks (\pm 5 days), thereafter. Patients will attend the extended follow-up visits until disease progression occurs based on RECIST Version 1.1 (see Appendix B) or another withdrawal criterion is met such as:

- Start of a new anti-cancer therapy
- Lost to follow-up
- Death
- Patient withdrawal
- End of the whole study.

CONFIDENTIAL

Study Drug: AC699 Sponsor/Development Innovations Study Numbers: AC699-001/BRE 401

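### SAP 5.2.4 does not start the missed-scan interval at first dose, so a week-16 progression after one missed scan can be censored before Day 1

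*SAP*

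**What the plan says.** - **The test.** SAP 5.2.4 decides whether at least two assessments are missing "based on the interval between the last evaluable tumor assessment date and the event date". For the first 52 weeks, "therefore, the threshold will be 18 weeks"; after that it is 34 weeks. Day 1 is not mentioned.
- **The outcome.** In SAP Table 4, "Progression documented between scheduled visits, or after one missed or non-evaluable assessment" is an event at the progression date. Progression after two or more missed assessments is censored at the last evaluable assessment. The first-dose date is used only when there is no baseline assessment.
- **What counts as evaluable.** SAP Table 2 takes the latest lesion data "where the overall response is evaluable (i.e., not missing or NE), prior to further subsequent anticancer therapy if initiated". It does not say whether the baseline scan qualifies.
- **Time origin.** SAP 5.1.2: "For all time to event variables other than DoR, the date of first dose of AC699 will be used as the start date".
- **Scan calendar.** Protocol, Schedule of Assessments, tumour assessment footnote: "Response will be assessed every 2 cycles / 8 weeks (±5 days) for the first 1 year of treatment", and "Baseline tumor assessments must be performed within 28 days before first drug intake". Protocol 7.4.3 counts the extended follow-up scans "from the patient's initial Cycle 1 Day 1 visit".

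**The concern.** The scan calendar and the PFS clock both start at first dose, but the missed-scan test starts at the last evaluable scan. Once a patient has an evaluable post-baseline scan, the difference is harmless. Before that, the only candidate is the baseline scan, and its lead of up to 28 days is added to the interval as if it were follow-up time.

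Two patients with the same on-study course (week-8 scan missed or not evaluable, progression at week 16) can then get opposite PFS outcomes solely because their screening scans were booked on different days. The one who is censored gets a date before PFS begins. That is not a valid survival time, so a documented progression at about 3.7 months contributes nothing to the Kaplan-Meier estimate for its dose level.

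**Working it through.** **1. The SAP's thresholds.** The text describes twice the assessment interval plus the allowed window. Three readings, in year 1 and then later:
- 2 × 56 + 5 = 117 days (16.7 weeks); 2 × 112 + 5 = 229 days (32.7 weeks).
- 2 × (56 + 5) = 122 days (17.4 weeks); 2 × (112 + 5) = 234 days (33.4 weeks).
- Window rounded to one week and counted twice: 2 × (8 + 1) = 18 weeks; 2 × (16 + 1) = 34 weeks.

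The third matches the stated 18 and 34 weeks exactly; the second matches if rounded up to whole weeks. I use 18 weeks = 126 days.

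**2. Interval for one missed scan.** Let b be the days from baseline scan to first dose (up to 28). The week-8 scan is missed and progression is found at week 16, 112 days after first dose (107 to 117 with the ±5-day window). If the baseline scan is the last evaluable assessment, the interval is 112 + b at nominal week 16:
- b = 1: 113 days, event.
- b = 14: 126 days, not above the limit, event.
- b = 15: 127 days, classed as two or more missed, censored.
- b = 28: 140 days, censored.

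**3. PFS when censored at the baseline scan.** PFS = (end - start + 1)/30.4375 = (1 - b)/30.4375 months.

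| Progression, days after first dose | Censored when | PFS (months) |
|---|---|---|
| 107 | b ≥ 20 | -0.62 to -0.89 |
| 112 | b ≥ 15 | -0.46 to -0.89 |
| 117 | b ≥ 10 | -0.30 to -0.89 |

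The smallest lead that can trigger censoring is 10 days: (1 - 10)/30.4375 = -0.30. If the threshold were read as 122 or 117 days, censoring at nominal week 16 would start at b = 11 or b = 6.

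**4. Baseline scan not counted.** Read strictly, Table 2 needs an overall response, which a baseline scan does not have. There is then no start date for the interval, and the 18-week test returns nothing.

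**5. Share of such patients affected (assumption, not a document figure).** With b spread evenly over 1 to 28 days, the censored share is 9/28 = 32%, 14/28 = 50% or 19/28 = 68% for progression at day 107, 112 or 117. If every baseline scan falls within 14 days of first dose and the week-16 scan is spread evenly over the window, it is about 10%.

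**6. Effect on one dose group.** In a group of N with no other censoring, let k patients be progression-free just after week 16. Losing the patient changes the estimate from k/N to k/(N - 1), a rise of k/[N(N - 1)]. This is at most 1/N: 5.0 points for N = 20 (Protocol expansion size) and 6.7 points for N = 15 (SAP expansion size).

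**7. With the interval started no earlier than first dose.** The interval is 112 days (107 to 117), below 126 for every permitted baseline date. The patient is an event at (112 + 1)/30.4375 = 3.71 months (3.55 to 3.88). A patient who really misses weeks 8 and 16 and progresses at week 24 has an interval of 168 days (at least 163 in window), so the two-missed rule still applies.

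**The case against.** The best defence is that the SAP already points to an event. The one-missed row of Table 4 describes this patient, and SAP 5.1.2 gives events precedence over censoring. On the strict reading of Table 2 the baseline scan is not an evaluable assessment at all, so the 18-week test cannot class the patient as missing two scans, and the one-missed row is what remains.

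Part of this stands: the text contradicts itself and does not clearly order censoring. It does not dispose of the point. SAP 5.2.4 makes the interval the test that selects between the two rows, so a programmer who counts the baseline scan will censor. The precedence rule, applied literally, would cancel the two-missed row for every patient, so it cannot settle this one. The strict reading leaves the test undefined, which also needs a sentence.

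The defence is stronger on size. Protocol Appendix B asks for baseline imaging as near to treatment start as possible, so an even spread over 28 days is pessimistic. The Efficacy Evaluable Set requires an adequate post-baseline assessment, so most patients with no usable post-baseline scan are not in the PFS analysis. Our patient is, because the week-16 progression scan qualifies.

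**Conclusion.** Wrong as written, minor severity. If the baseline scan counts as the last evaluable assessment and was more than about two weeks before first dose (b ≥ 15 at nominal week 16; the cut-off runs from 10 to 20 days across the visit window), the rule censors a progression that Table 4 calls an event. The resulting PFS is -0.30 to -0.89 months. If the baseline scan does not count, the rule gives no classification.

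A reader might infer more than the documents support:
- **That every week-16 progression after one missed scan is censored.** It depends on the lead; with a later baseline scan the same patient is an event.
- **That PFS is both negative and undefined.** These belong to different readings of Table 2. On the second, the interval test does not itself produce censoring.
- **That a known number of events is lost.** The documents give no rate for missing week 8 and then progressing at week 16, and any percentage rests on an assumed spread of baseline dates. The frequency is likely low.
- **That PFS is biased upward throughout.** Dropping the patient also removes someone progression-free until week 16, so the curve is the same or slightly lower before then and higher only afterwards.
- **That patients starting new anticancer therapy before any evaluable scan are a large second group.** New therapy ends study participation and extended follow-up (Protocol 5.3 and 7.4.3), so a later qualifying scan would be unusual.

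PFS is a secondary endpoint with no hypothesis test. The point still deserves correction because it is summarised by dose level, where one event can move the estimate by up to 5 to 7 points.

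**What to change.** In SAP 5.2.4:
- Measure the gap from the later of the first dose of AC699 and the last evaluable tumour assessment.
- State that no censoring date may precede the first dose, and that the first-dose date is used when there is no evaluable post-baseline assessment before the censoring rule applies. A matching row in Table 4 would make this visible.

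This settles both readings of Table 2 and brings the interval test into line with the one-missed row. Duration of response is unaffected, because a responder already has an evaluable scan after first dose. The cost is two sentences and, if wanted, one table row, with no new data and no change to the scan schedule.

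### For gaps that span the week-52 schedule change, the 18- and 34-week thresholds in SAP 5.2.4 misclassify some PFS and DoR outcomes against Table 4 under each natural way of choosing between them

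*SAP*

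**What the plan says.** Table 4 in SAP 5.2.4 sets the outcome by the number of missed assessments. An event at the progression date is assigned to: "Progression documented between scheduled visits, or after one missed or non-evaluable assessment". A parallel row makes a death after one missed assessment a PFS event. The opposite row reads "Death, or progression after two or more missed tumor assessments" and censors at the last evaluable assessment. DoR (SAP 5.2.3) refers to the same table.

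The SAP does not count scans to apply these rows. The determination is "based on the interval between the last evaluable tumor assessment date and the event date". The test is: "If the interval is greater than twice the protocol-specified interval between the tumor assessment plus the protocol-allowed time window around the assessment", in which case two or more are taken as missed. For the first 52 weeks, "therefore, the threshold will be 18 weeks"; after the first 52 weeks, "therefore, the threshold will be 34 weeks". The SAP does not say whether the last evaluable date or the event date selects the threshold, and it has no provision for a gap with one end on each side of week 52.

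Protocol 7.3.4 and the Schedule of Assessments give scans every 8 weeks in the first year and every 16 weeks afterwards, each within 5 days. They do not state the week of the first scan after week 48. For patients off treatment, protocol 7.4.3 counts from the "initial Cycle 1 Day 1 visit) for the first year and then every 16 weeks", whereas SAP 5.1.3 applies the 8-weekly schedule "for the first year after treatment ends".

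**The concern.** A single gap length can stand in for a count of missed scans only while the spacing is constant. Around week 52 the spacing doubles. A gap that reflects two missed scans on the 8-weekly schedule can reflect only one across the change. A threshold suited to the 16-weekly schedule can in turn let two or three missed 8-weekly scans pass.

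If the rule over-censors, documented progressions after one missed scan are discarded. If it under-censors, late progressions or deaths that the plan meant to censor are counted at their late dates. The patients concerned are those still progression-free near one year, where the PFS and DoR curves rest on few people. Because the SAP leaves the choice of threshold open, the programmer would have to make it, possibly with the data in view.

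**Working it through.** **Inputs.** Scan intervals of 8 and 16 weeks and a 5-day window (protocol 7.3.4, SAP 5.2.4); thresholds of 18 and 34 weeks (SAP 5.2.4); event and censoring rows (SAP Table 4). *Assumption:* scans at weeks 8, 16, 24, 32, 40, 48, then 64, 80 and every 16 weeks. Week 64 is not in the documents, so weeks 52, 56 and 68 are also tried. A scan counts as missed once its +5-day window has closed.

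**1. The SAP's own thresholds reproduce.**
- 2 × (56 + 5) days = 122 days = 17.43 weeks, rounded up to 18.
- 2 × (112 + 5) days = 234 days = 33.43 weeks, rounded up to 34.
- With the window added only once, 117 days (16.71 weeks) and 229 days (32.71 weeks) would round up to 17 and 33. The stated figures therefore count the window twice.

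**2. Within a single schedule the rule works.** Progression at a scheduled visit after one missed scan has a gap of 16 or 32 weeks, inside 18 or 34, so it is an event. After two missed scans the gap is 24 or 48 weeks, outside, so it is censored. Both agree with Table 4. The only slack is for deaths: the second missed window closes at day 117 (or 229), but the limit is day 126 (or 238). A death in those 9 days counts although two scans were missed.

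**3. Across week 52, with the next scan at week 64.**

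| Last scan → event | Missed | Gap (weeks) | Table 4 | By last-scan date | By event date | By interval after last scan |
|---|---|---|---|---|---|---|
| 40 → PD 64 | 1 (48) | 24 | event | >18, **censored** | ≤34, event | >18, **censored** |
| 48 → PD 80 | 1 (64) | 32 | event | >18, **censored** | ≤34, event | ≤34, event |
| 32 → PD 64 | 2 (40, 48) | 32 | censored | >18, censored | ≤34, **event** | >18, censored |
| 24 → death 53 | 3 (32, 40, 48) | 29 | censored | >18, censored | ≤34, **event** | >18, censored |

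Bold marks disagreement with Table 4. Scanning death dates day by day gives:
- By last-scan date, deaths after one missed scan are wrongly censored in about weeks 58.1–64.7 (last scan week 40) and 66.1–80.7 (last scan week 48).
- By event date, deaths in about weeks 52.1–58.0 after a week-24 scan are wrongly counted, with three scans missed.
- The event-date reading also jumps at week 52. After a week-32 scan, a death at week 51 (gap 19 > 18) is censored, while one at week 53 (gap 21 ≤ 34) is an event. Two scans are missed in both cases.

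**4. Other positions of the first later scan.** Scheduled-visit progressions that disagree with Table 4:

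| Scans after week 48 | By last-scan date: wrongly censored | By event date |
|---|---|---|
| 52, 68, 84 | 48→68 (20 weeks, 1 missed); 52→84 (32, 1 missed) | 40→68 (28, 2 missed) wrongly counted |
| 56, 72 | 48→72 (24, 1 missed) | 24→56 (32, 3 missed), 32→56 (24, 2 missed), 40→72 (32, 2 missed) wrongly counted |
| 68, 84 | 40→68 (28, 1 missed); 48→68 (20, none missed); 48→84 (36, 1 missed) | 48→84 (36 > 34, 1 missed) wrongly censored |

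Both readings fail on every grid tried.

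**5. The off-treatment clock.** Suppose treatment stops at week 30. On the SAP 5.1.3 wording, 8-weekly scans continue to about week 30 + 52 = 82, for example at weeks 48, 56, 64, 72 and 80. A progression at week 80 after a week-48 scan then follows three missed scans with a gap of 32 weeks. By event date it faces the 34-week limit and is counted. On the protocol's clock, with the next scan at week 64, the same dates represent one missed scan.

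**The case against.** The strongest reply is that the gap is the SAP's operational definition of a missed assessment. Table 4 does not say how to count, so a proxy that is imprecise at one schedule change does not contradict it. Reading the protocol-specified interval as the one in force after the last scan repairs most of the damage. Part of this stands: on the week-64 grid that third reading leaves only gaps from week 40 wrong among scheduled-visit progressions. But it is not written in the SAP, and it still censors a progression at week 64 after a single missed scan, which Table 4 plainly calls an event. The SAP 5.1.2 rule that events outrank censoring does not help either, since applied here it would cancel the censoring row altogether.

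It is also fair that the week-64 grid is an assumption. The particular pairs depend on it; the failure of the first two readings does not, within the positions tried.

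The SAP 5.1.3 wording is a separate inconsistency. That section defers to protocol 7.4.3 and does not define the 52 weeks used with Table 4. It matters here because counting missed scans needs one agreed grid.

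A reader might infer that the 18- and 34-week figures are miscalculated, or that the rule fails throughout. The documents do not support this: the figures reproduce, and within one schedule they agree with Table 4 for every scheduled-visit progression.

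**Conclusion.** The concern holds for gaps that span the change from 8- to 16-weekly scans. There the stated rule gives results at odds with Table 4: too much censoring if the last-scan date selects the threshold and, on the week-64 grid, too little if the event date does. Using the interval in force after the last scan reduces the error without removing it.

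The named pairs rest on a week-64 scan. The finding that the last-scan-date and event-date readings both fail also holds for weeks 52, 56 and 68.

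The reach is narrow: patients still at risk near one year who also missed scans. The documents do not say how many there will be. A reader might infer that the PFS median or the upper quartile would visibly move. Nothing in the documents allows that to be calculated, and it is not claimed. PFS and DoR are secondary and descriptive, with no hypothesis test, and the primary safety endpoints are untouched. This should be corrected before database lock, but it does not threaten the trial's main conclusions.

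**What to change.** In SAP 5.2.4, for both PFS and DoR:
- List the scheduled scan weeks from Cycle 1 Day 1, including the first scan after week 48.
- Count missed scheduled assessments directly, at least for any gap that spans week 52. A scan is missed once its +5-day window closes without an evaluable assessment.

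Separately, reconcile SAP 5.1.3 with protocol 7.4.3 so that the first year has one starting point.

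A revised set of day limits keyed to the last scan is a tempting shortcut, for example 122 days up to week 32, 178 days for week 40 and 234 days from week 48. It is not equivalent to counting. After a week-32 scan the week-48 window closes at day 117, so a death on days 118–122 would count despite two missed scans. If the later scans fall at weeks 68 and 84, progressions after one missed scan at 40→68 (196 days > 178) and 48→84 (252 days > 234) would still be censored.

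The cost is a short change of SAP wording in two sections and one derivation. No new data are needed.
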